# 10.4.2 Safety analyses

### **10.4.2.1** Analysis set and grouping for the analyses

For primary safety analyses, the safety set will be used.

The assessment of safety will be based mainly on the frequency of adverse events and on the number of laboratory values that fall outside of pre-determined ranges. Other safety data (e.g., ECG, vital signs) will be considered as appropriate. All safety data will be listed.

The overall observation period will be divided into three mutually exclusive segments:

1. Pre-treatment period: from day of ICF signature to the day before first dose of bimiralisib

- 2. On-treatment period: from day of first dose of bimiralisib to 30 days after last dose of bimiralisib
- 3. Post-treatment period: starting at day 31 after last dose of bimiralisib

# 10.4.2.2 Adverse events (AEs)

Summary tables for adverse events will include only adverse events that started or worsened during the on-treatment period, i.e. *treatment-emergent* adverse events.

The incidence of treatment-emergent adverse events (new or worsening from baseline) will be summarized by system organ class and/or preferred term, severity (based on CTCAE version 5.0 grades), type of adverse event, relation to study treatment by treatment arm. Deaths reportable as serious adverse events and non-fatal serious adverse events will be listed by patient and tabulated by type of adverse event and treatment arm.

Serious adverse events and non-serious adverse events during the on-treatment period will be tabulated.

All deaths (on-treatment and post-treatment) will be summarized.

All AEs, deaths and serious adverse events (including those from the pre and post-treatment periods) will be listed and those collected during the pre-treatment and post-treatment period will be flagged.

### **10.4.2.3** Laboratory abnormalities

For laboratory tests covered by the CTCAE version 5.0, the study's biostatistical and reporting team will grade laboratory data accordingly. For laboratory tests covered by CTCAE, a grade 0 will be assigned for all non-missing values not graded as 1 or higher. Grade 5 will not be used.

For laboratory tests where grades are not defined by CTCAE, results will be graded by the low/normal/high classifications based on laboratory normal ranges. All low or high results must be accompanied by a designation of "NCS" in case the result is not clinically significant, or "CS" if the result is clinically significant. Clinically significant result must be reported as (S)AE – if available, the underlying diagnosis should be reported.

The following by-treatment summaries will be generated separately for hematology and biochemistry laboratory tests:

- Number and percentage of patients with worst post-baseline CTCAE grade (regardless of the baseline status)
- Shift tables using CTCAE grades to compare baseline to the worst on-treatment value
- For laboratory tests where CTCAE grades are not defined, shift tables using the low/normal/high/(low and high) classification to compare baseline to the worst on-treatment value.

- Listing of all laboratory data with values flagged to show the corresponding CTCAE grades, the classifications relative to the laboratory normal ranges, and the "NCS" or "CS" designation.
- Listing of all notable laboratory abnormalities (i.e., newly occurring CTCAE grade 3 or 4 laboratory toxicities)

In addition to the above mentioned tables and listings, other exploratory analyses, for example figures plotting time course of raw or change in laboratory tests over time or box plots might be specified in the statistical analysis plan.

Laboratory values collected later than 30 days after last dose of bimiralisib will be flagged in the listings.

# **10.4.2.4** ECG and other safety data

Summary statistics for data from other tests will be provided, notable values will be flagged, and any other information collected will be listed as appropriate.

Summary statistics will be provided for:

- ECGs: changes from baseline
- Vital signs: number and percentage of patients with at least one post-baseline vital sign abnormality

Listings with flagged notable values and any other information collected will be provided as appropriate.

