	
 
SAEs resulting in death
 

	
 
SAEs resulting in discontinuation
 

	• SAEs resulting in dose reduction or dose interruption
	• Frequency, time to onset and severity of AEs
	• Changes from baseline in safety parameters
	
 
Additional Efficacy: TTR, DOR, TTF and PFS, evaluated according to the response evaluation criteria in solid tumors (RECIST), version 1.1 [2, 3]
 
Pharmacokinetics: Bimiralisib plasma concentrations. To be reported separately.
 

F _1_4	
Exploratory	• ctDNA:
endpoints	
 
ctDNA sequences and levels in patient plasma
 

	Pre-cancerous keratinocytic skin lesions:
	• Number and size of index lesions
	NOTCH protein levels
	
 
Protein levels
 
Protein levels of cleaved NOTCH1 (NICD) as determined by immunohistochemistry (IHC)
 

Version 5.0

Study design	This is an open-label, single arm, two-stage study to evaluate the efficacy and safety of bimiralisib in patients with r/m HNSCC containing NOTCH1 LOF mutations. The study will be conducted in $1 - 4$ centers. Patients will be treated with 140 mg bimiralisib p.o. once daily on two consecutive days followed by five days without treatment in consecutive 7-day treatment blocks. Patients will follow this iterative "2d on / 5d off" treatment scheme until unacceptable toxicity, tumor progression, patient's request for withdrawal, investigator judgment or death, whichever comes first.
	Stage 1 of the study will enroll 10 patients. Response evaluation of Stage 1 patients will be performed in an ongoing manner (ongoing analysis, OA). If two or more patients in stage 1 show a confirmed partial or confirmed complete response, stage 2 may enroll 19 patients. If less than two patients in stage 1 show a confirmed partial or confirmed complete response during the OA, a formal futility analysis will be performed once all 10 patients in Stage 1 have been assessed for their response to bimiralisib. If futility is confirmed as per defined criteria, the study will be stopped.
	The study will end when all patients have been treated for 6 months or have discontinued study participation for any reason, whichever comes first.
Patient population	Adult patients with recurrent or metastatic HNSCC with NOTCH1 LOF mutations

Inclusion criteria	Patients may be included in the study if they meet all the below inclusion criteria:

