### **3** Study purpose, objectives and endpoints

The main purpose of this study is to determine the objective response rate (ORR) of patients with r/m HNSCC harboring *NOTCH1* LOF mutations to oral bimiralisib. The ORR comprises patients with confirmed partial response (PR) or confirmed complete response (CR) as per RECIST version 1.1 [2, 3].

The study objectives and related endpoints are summarized in Table 3.

Protocol PQR309-009

PIQUR Therapeutics AG - Confidential

Version 5.0

Amendment date: see date of last approval

Table 3:Objectives and related endpoints

I able 3: Objectives and related enapoints		
Objective(s)	Endpoint(s)	Assessment Description
Primary		
To determine the objective response rate (ORR) of patients with r/m HNSCC harboring NOTCH1 LOF mutations to oral bimiralisib	ORR: comprised of all patients who achieved a confirmed partial or a confirmed complete response	Section 9.3
Secondary		
To evaluate the safety of bimiralisib in patients with r/m HNSCC harboring NOTCH1 LOF mutations	
 
Overall SAEs
 
Overall SAEs
 
SAEs resulting in death
 
SAEs resulting in discontinuation
 
SAEs resulting in dose reduction or dose interruption
 
SAEs resulting in dose reduction or dose interruption
 
Changes from baseline in:
 
body weight,
 
vital signs,
 
ECOG performance status,
 
ECO,
 
hematology,
 
hematology,
 
biochemistry and
 
Patient Health Questionmaire (PHQ)-9 and General Anxiety Disorder (GAD)-7 mood scale score
 
	Section 9.4

Page 23 of 81

Protocol PQR309-009 PI	PIQUR Therapeutics AG - Confidential	Version 5.0
	Amendm	Amendment date: see date of last approval
Objective(s)	Endpoint(s)	Assessment Description
To evaluate additional clinical efficacy parameters of bimiralisib in patients with r/m HNSCC harboring NOTCH1 LOF mutations	TTR, DOR, TTF and PFS, evaluated according to RECIST version 1.1 [2, 3].	Section 9.3
To evaluate the pharmacokinetics of bimiralisib in patients with r/m HNSCC harboring NOTCH1 LOF mutations	Bimiralisib plasma concentrations. To be reported separately.	Section 9.6
Exploratory		
To determine if bimiralisib affects the size and number of pre-cancerous keratinocytic lesions (actinic keratosis)	Number and size of index lesions	Section 9.7.1

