# 9.4.2 Vital signs

Vital signs (body temperature, pulse rate, blood pressure) will be monitored as per the visit schedule (Table 2).

Blood pressure (systolic and diastolic) and pulse should be measured in sitting position. Clinically significant findings that were present prior to first bimiralisib intake must be included in the relevant medical history/current medical conditions page on the CRF. Relevant new findings that begin or worsen after first bimiralisib intake and meet the definition of an AE must be recorded on the adverse event page of the CRF.

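### Change from baseline in vital signs is a secondary safety endpoint, but the only vital-sign summary specified is an ever-abnormal count with no baseline condition

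*Protocol*

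**What the plan says.** The secondary safety endpoints in Protocol section 3 (Table 3) include a list introduced by "Changes from baseline in". It covers body weight, vital signs, ECOG performance status, ECG, hematology, biochemistry, and the PHQ-9 and GAD-7 scores. The synopsis (section 1.1) puts it more generally: "Changes from baseline in safety parameters".

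Section 10.4.2.4 begins with a general promise of summary statistics for other tests, then names two items. The first is "ECGs: changes from baseline". The second is "Vital signs: number and percentage of patients with at least one post-baseline vital sign abnormality".

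For laboratory tests, section 10.4.2.3 plans a worst-grade count that ignores baseline, but pairs it with "Shift tables using CTCAE grades to compare baseline to the worst on-treatment value". Vital signs have no such companion table. Section 10.4 leaves detailed data handling to the SAP. The SAP text available covers only the hypotheses and the sample size.

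**The concern.** The endpoint and the named statistic measure different things. Change from baseline asks how far each patient moved from the pre-dose value. The specified count asks whether a patient was ever abnormal afterwards.

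Two features make the count hard to use in this trial:

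- **Baseline status.** Nothing in the wording excludes a patient whose reading was abnormal before dosing and stayed the same.
- **Length of observation.** Patients are treated until progression, toxicity or withdrawal, so the number of readings differs between patients. More readings give more chances of one abnormal value, so patients who stay on treatment longest, responders among them, tend to contribute more.

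A control arm would show the background level. This trial has none. At stake is whether one declared secondary safety endpoint has a matching analysis, and whether the table produced in its place can be interpreted.

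**Working it through.** **Step 1. Endpoint against planned summary (Protocol).**

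| Data | Endpoint | Summary named in 10.4.2 | Baseline comparison |
|---|---|---|---|
| Adverse events | Frequency, onset, severity | Treatment-emergent tables (10.4.2.2) | Yes: new or worsened only |
| Laboratory | Change from baseline | Worst grade plus shift tables (10.4.2.3) | Yes |
| ECG | Change from baseline | Change from baseline (10.4.2.4) | Yes |
| Vital signs | Change from baseline | Ever abnormal after baseline (10.4.2.4) | None stated |
| Body weight, ECOG, PHQ-9/GAD-7 | Change from baseline | None named | Not specified |

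Vital signs are the only row where a summary is named but involves no comparison with baseline.

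**Step 2. Inputs for an illustration.** The plan states no figure for vital signs, so there is none to reproduce.

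- Denominator: the safety set, meaning everyone who took at least one dose (10.3.1). The design number is 29. With the plan's 20% allowance, 29 × 1.2 = 34.8, the stated maximum of 35 (10.2).
- Visits (Table 2): a patient with readings at Days 8, 15, 22 and 43 and at end of treatment has k = 5. Adding Days 64 and 85 and week 18 gives k = 8. Day 1 is left out because the plan does not say whether that reading precedes the dose.
- Assumed, not in the documents: b, the share persistently abnormal from baseline (10% to 30%), and q, the chance of an abnormal reading per visit with no drug effect (2% to 10%). Visits are treated as independent.

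**Step 3. Pre-existing abnormality alone.** If 3, 6 or 9 of 35 treated patients are persistently abnormal, the count shows 3/35 = 9%, 6/35 = 17% or 9/35 = 26%.

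**Step 4. Number of visits alone (patients normal at baseline).** P(at least one) = 1 − (1 − q)^k.

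| q | k = 5 | k = 8 |
|---|---|---|
| 2% | 9.6% | 14.9% |
| 5% | 22.6% | 33.7% |
| 10% | 41.0% | 57.0% |

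Positive correlation between a patient's readings lowers these values. In the extreme of perfect correlation the probability stays at q for any k. For q = 5% and k = 5 the range is therefore 5% to 22.6%.

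**Step 5. Both together.** Expected proportion = b + (1 − b)[1 − (1 − q)^k].

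- b = 20%, q = 5%, k = 5: 0.20 + 0.80 × 0.226 = 0.381, about 13 of 35.
- b = 20%, q = 5%, k = 8: 0.20 + 0.80 × 0.337 = 0.469, about 16 of 35.
- Lowest at k = 5 (b = 10%, q = 2%): 0.10 + 0.90 × 0.096 = 0.186.
- Highest at k = 5 (b = 30%, q = 10%): 0.30 + 0.70 × 0.410 = 0.587.

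**Step 6. What a baseline condition removes.** Restricting to patients normal at baseline takes out b but leaves the Step 4 values. At q = 5% they still rise from 22.6% to 33.7% between 5 and 8 visits. A baseline-to-worst table therefore has to be read with exposure beside it. A by-visit change summary does not accumulate in this way.

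**The case against.** The strongest reply is that this is a drafting mismatch in a minor table. Several parts of it stand.

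- **The wording does not say that baseline is ignored.** A reader might infer that section 10.4.2.4 defines the count irrespective of baseline. That phrase appears only for laboratory grades in 10.4.2.3. For vital signs, an abnormality is left undefined. What can be said is that no baseline condition is set.
- **Misreading as toxicity is limited by the rest of the plan.** A reader might infer that pre-existing abnormality will be reported as drug toxicity. Section 9.4.2 sends clinically significant findings present before the first dose to medical history. Only findings that begin or worsen later and meet the definition become adverse events, and 10.4.2.2 tabulates only new or worsened events. Section 10.4.2.1 rests the safety assessment mainly on adverse events and laboratory values, gives vital signs a supporting role, and has all safety data listed.
- **The endpoint may still be produced.** The two-item list may not be exhaustive, since body weight, ECOG and the mood scores have no item either. The general promise of summary statistics could cover change from baseline. The documents thus support saying that the analysis is not specified, and not that it will be absent.

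The reply does not remove the point. The general sentence names no statistic. The specific item does, and it is not the one Table 3 calls for. The SAP text available does not fill the gap.

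**Conclusion.** The point holds in a limited form. Table 3 and section 10.4.2.4 do not match for vital signs. The one statistic named does not estimate the stated endpoint, can include patients abnormal before dosing, and tends to grow with the number of visits. In a single-arm trial it says little about the drug.

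The consequence is confined to a descriptive, supportive summary. The primary endpoint is untouched. The futility rule depends on responses only, and the data named for ongoing review in section 12.1.8 do not include vital signs. The change is worth making because it is cheap and a declared endpoint lacks a specified analysis. The trial's conclusions are not threatened.

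The size is not known. Under the assumed rates, the count at 5 visits could lie between 19% and 59% with no drug effect. This rests on assumed b and q and on independent readings. Correlation would pull it down, and the documents offer no way to choose within the range.

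**What to change.** In Protocol section 10.4.2.4, and in the SAP:

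1. Add change from baseline by visit for each vital sign, as for ECG, with the number of patients at each visit. Define baseline as the last pre-dose value: Day -1, or Day 1 if taken before dosing. Table 2 schedules readings on both days and the plan does not choose.
2. Add a table of baseline against worst on-treatment value for each vital sign. Show newly abnormal or worsened patients separately, state what counts as abnormal, and display the number of visits or exposure alongside.
3. Keep the ever-abnormal count, if wanted, as a supplementary output or listing.
4. Give body weight, ECOG status, PHQ-9 and GAD-7 the same change-from-baseline summary, since Table 3 lists them too.

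For vital signs the cost is a few sentences and one or two extra tables; item 4 adds simple summaries of the same kind. All of it uses data already scheduled for collection, with no new visits. The downside is that pre-existing, unchanged abnormalities leave the headline count and appear only in the supplementary output. Neither new table creates a comparator, so attribution to the drug will still rest on judgement.

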# 10.4.2.5 Tolerability

Tolerability will be studied in terms of dose reductions and drug interruptions due to AE. Reasons for dose reductions and interruptions will be listed and summarized by treatment.

# 10.4.3 Other analyses

### **10.4.3.1** Pharmacokinetics

Bimiralisib concentrations in plasma will be determined by a validated HPLC method.

No formal statistical analysis beyond descriptive statistics is planned. For each PK parameter, individual and mean data and summary statistics will be presented.

Data will be reported separately.

# **10.4.3.2** Exploratory Analyses

Exploratory analyses will be reported separately.

# **12** Supporting documentation and operational considerations

# 12.1 Appendix 1: Regulatory, ethical, and study oversight

# **12.1.1** Regulatory and ethical considerations

This clinical study was designed, shall be implemented and reported in accordance with the ICH harmonized tripartite guidelines for good clinical practice, with applicable local regulations (including US Code of Federal Regulations title 21), and with the ethical principles laid down in the declaration of Helsinki.

The protocol and the proposed informed consent form must be reviewed and approved by a properly constituted institutional review board/independent ethics committee (IRB/IEC) before study start. Prior to study start, the investigator is required to sign a protocol signature page confirming his/her agreement to conduct the study in accordance with these documents and all of the instructions and procedures found in this protocol and to give access to all relevant data and records to PIQUR monitors, auditors, PIQUR clinical quality assurance representatives, designated agents of PIQUR, IRB/IEC and regulatory authorities as required.

# 12.1.2 Quality control and quality assurance

Several procedures ensure the quality of the trial in compliance with applicable regulatory requirements, GCP and the protocol:

- Written standard operating procedures are implemented
- Personnel involved in conducting the trial is qualified by education, training and experience
- An updated authorization list must be kept at the site
- Use of validated computerized systems to manage the clinical trial (e.g. pharmacovigilance, clinical database, CRF, statistical analysis, TMF
- On-site monitoring (SDV, verification of informed consent etc.) by personnel designated by the sponsor
- Data captured online will be validated in real-time, yielding errors (for inacceptable data) and warnings (for possibly inconsistent data these warnings may be overruled by the user)
- Audit trail of changes
- Safety monitoring
- Accountability of PQR309.

# 12.1.3 Financial disclosure

Financial disclosures should be provided by study personnel who are directly involved in the treatment or evaluation of patients at the site - prior to study start.

### **12.1.4** Informed consent process

Eligible patients may only be included in the study after providing written (witnessed, where required by law or regulation), IRB/IEC-approved informed consent.

Informed consent must be obtained before conducting any study-specific procedures (i.e. all of the procedures described in the protocol). The process of obtaining informed consent should be documented in the patient source documents. The date when a patient's informed consent was obtained will be recorded in the CRF.

PIQUR will provide to investigators, in a separate document, a proposed informed consent form (ICF) that is considered appropriate for this study and complies with the ICH GCP E6 (R2) guideline and regulatory requirements. Any changes to this ICF suggested by the investigator must be agreed to by PIQUR before submission to the IRC/IEC, and a copy of the approved version must be provided to the PIQUR monitor after IRC/IEC approval.

Women of child bearing potential should be informed that taking the study medication may involve unknown risks to the fetus if pregnancy were to occur during the study and agree that in order to participate in the study they must adhere to the contraception requirement for the duration of the study up to 90 days after last intake of bimiralisib. If there is any question that the patient will not reliably comply, they should not be entered in the study.

# 12.1.5 Data protection

Information about study patients will be kept confidential and managed under the applicable laws and regulations. Those regulations require a signed patient authorization informing the patient of the following:

- What protected health information (PHI) will be collected from patients in this study
- Who will have access to that information and why
- Who will use or disclose that information
- The rights of a patient to revoke their authorization for use of their PHI.

In the event that a patient revokes authorization to collect or use PHI, the investigator, by regulation, retains the ability to use all information collected prior to the revocation of patient authorization. For patients that have revoked authorization to collect or use PHI, attempts should be made to obtain permission to collect follow-up safety information (e.g. has the patient experienced any new or worsened adverse events) at the end of their scheduled study period.

The data collection system for this study uses built-in security features to encrypt all data for transmission in both directions, preventing unauthorized access to confidential participant information. Access to the system will be controlled by a sequence of individually assigned user identification codes and passwords, made available only to authorized personnel who have completed prerequisite training.

Year of birth will be solicited (in the place of exact date of birth) to establish that the patient satisfies protocol age requirements and to enable appropriate age-related normal ranges to be used in assessing laboratory test results.

# **12.1.6** Source documents

Each participating site will maintain appropriate medical and research records for this trial, in compliance with section 4.9 of the ICH GCP E6 (R2), and regulatory and institutional requirements for the protection of confidentiality of patients. As part of participating in a PIQUR-sponsored study, each site will permit authorized representatives of the sponsor(s) and regulatory agencies to examine (and when required by applicable law, to copy) clinical records for the purposes of quality assurance reviews, audits and evaluation of the study safety and progress.

Source data are all information, original records of clinical findings, observations, or other activities in a clinical trial necessary for the reconstruction and evaluation of the trial. Examples of these original documents and data records include, but are not limited to, hospital records, clinical and office charts, laboratory notes, memoranda, patients' diaries or evaluation checklists, pharmacy dispensing records, recorded data from automated instruments, copies or transcriptions certified after verification as being accurate and complete, microfiches, photographic negatives, microfilm or magnetic media, x-rays, and patient files and records kept at the pharmacy, at the laboratories, and medico-technical departments involved in the clinical trial.

Data collection is the responsibility of the clinical trial staff at the site under the supervision of the site principal investigator. The study CRF is the primary data collection instrument for the study. The investigator should ensure the accuracy, completeness, legibility, and timeliness of the data reported in the CRFs and all other required reports. Data reported on the CRF, that are derived from source documents, should be consistent with the source documents or the discrepancies should be explained. All data requested on the CRF must be recorded. Any missing data must be explained. For electronic CRFs an audit trail will be maintained by the system.

The investigator/institution should maintain the trial documents as specified in essential documents for the conduct of a clinical trial (ICH GCP E6 (R2) section 8) and as required by applicable regulations and/or guidelines. The investigator/institution should take measures to prevent accidental or premature destruction of these documents.

Essential documents (written and electronic) should be retained for a period of not less than fifteen (15) years from the completion of the clinical trial unless sponsor provides written permission to dispose of them or, requires their retention for an additional period of time because of applicable laws, regulations and/or guidelines.

